### **6.2.1 Randomization Methods**

Treatment assignments will be generated using a pseudo-random-number generator with randomly permuted blocks. This method serves to balance the treatment group assignments over the course of the study to ensure that the desired number of subjects will be allocated to each of the treatment groups at any time point during the randomization period. The statistical method for implementation of the randomization plan will be detailed in the Statistical Analysis Plan (SAP). Briefly, after obtaining informed consent, all eligibility confirmation data will be entered into the RAVE EDC database by the delegated study staff. If the subject meets all eligibility criteria, computer randomization will be performed and the coordinator will be provided with an audit trail of the process including a verifiable link between the unique study ID and treatment assignment. The application will be password protected with access restricted to designated MILES personnel.

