- e Only subjects that meet all eligibility criteria will undergo the Screening MRI
- f Investigator will aspirate synovial fluid prior to knee injection when possible (physician's discretion). Collected synovial fluid will be sent to MC3M for testing (details in study manuals).
- g PTT may be ordered if deemed appropriate by the treating investigator
- h CBC should include a platelet count
- i Basic metabolic panel and Liver function panel may be substituted for a Comprehensive metabolic panel (physician's discretion) as long as the test includes an ALT and Total Bilirubin
- j Assessments completed during an Unscheduled Visit will be at the discretion of the treating investigator based on the reason for visit and examination of the subject. Laboratory assessments may be ordered at the discretion of the treating investigator.
- k Observation of the harvest site will be completed at the 7-day follow-up and 30-day follow-up visits. This will only be done for subjects on Arm 1 and Arm 2.
- l Please refer to the Operations Manual for specific results required for this testing
- m End of study visit: Assessments required will be at the discretion of the treating investigator in order to ensure subject safety. The EOS visit would only occur in the event the study is discontinued early (see Section 7.5)
- n Optional, at the discretion of the treating investigator
- o Refer to the Operations Manual for Arm-specific product release criteria requirements.
- p Treating Investigator must complete the Pre-Treatment Confirmation of Subject Eligibility form PRIOR to procedure or UCT dispensing.
- q Only subjects randomized to Arm 1 or Arm 2.
- r Only subject randomized to receive the CSI treatment in any of the 3 arms.

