In order to accurately assess the efficacy of these treatments, routine follow-up examinations will be necessary. Follow-up exams will occur at intervals of 1 week, 1 month, 3 months, 6 months, 9 months (telephone only) and 1 year. After completing the screening and consent portion of the trial, the subjects will undergo a pre-injection MRI and then an additional MRI at 6 and 12 months. Additionally, subjects will fill out PROs at each time point.

The Marcus Center for Therapeutic Cell Characterization and Manufacturing (MC3M) at Georgia Institute of Technology will serve as a core cell analytics center for this clinical trial. MC3M's goal is to provide deep and broad characterization of all cells used in the trial, including synovial fluid, harmonize and standardize analytical and processing parameters across the different clinical sites and eventually, as patient outcome data become available, the MC3M will apply quantitative advanced modeling tools to identify predictive signatures of cell properties that correlate with efficacy and safety.

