#### **8.1 Study Visit Assessments**

##### **8.1.1 Screening Visit (Visit 1)**

- Administer informed consent and HIPAA Authorization
- Collect demography
- Collect medical and surgical history
- Collect prior and concomitant medications
- Collect Knee Osteoarthritis History
- Review inclusion and exclusion criteria
- Focused knee assessment
- Perform vital signs
- Knee MRI (only if the subject is eligible for the study)
- Collect subject PROs
- Perform pregnancy test (on female subjects of childbearing potential)
- Blood Collection (safety labs)
- Once all screening assessments are complete and eligibility has been confirmed by the treating investigator, the subject may be randomized.
- Schedule the subject for the appropriate Treatment Visit procedure based on randomization

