### **8.1.7 Month 9 Phone Call (Visit 7, Day 270)**

- Collect concomitant medications and treatments
- PROs
- Assess adverse events

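### The coordinator receives the product assignment at screening, and nothing keeps staff who know it away from collecting the pain scores, including those due at the Month 9 call

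*Combined protocol and SAP*

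**What the plan says.** **Who learns the assignment.** Section 6.2.1 says that after computer randomisation the "coordinator will be provided with an audit trail of the process including a verifiable link between the unique study ID and treatment assignment". Access to the application is limited in general terms ("access restricted to designated MILES personnel"), with no division into blinded and unblinded roles.

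**When.** The Schedule of Activities (1.3) places randomisation in the screening column. Section 8.1.1 agrees: "Once all screening assessments are complete and eligibility has been confirmed by the treating investigator, the subject may be randomized". The next step at the same visit is "Schedule the subject for the appropriate Treatment Visit procedure based on randomization". Footnote p of the Schedule then adds a Day 0 step: "Treating Investigator must complete the Pre-Treatment Confirmation of Subject Eligibility form PRIOR to procedure or UCT dispensing".

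**How the outcomes are collected.** Section 9.3.1 names VAS pain and KOOS pain as the primary variables, and 8.2.11 lists both instruments as patient-reported outcomes by title only. Section 4.1 states: "Additionally, subjects will fill out PROs at each time point". Section 8.1.7, headed "Month 9 Phone Call (Visit 7, Day 270"), includes these outcomes among the activities of the call. Section 9.3.2 uses baseline and Months 1, 3, 6, 9 and 12 as time levels in the primary mixed model.

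**Who is blinded.** Sections 4.1 and 6.2.2 describe a single-blind trial. The subject is the only party described as blinded.

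**The concern.** When the outcome is the subject's own pain rating and only the subject is masked, that mask is the endpoint's main protection. The sponsor invests in it: control subjects in Arms 1 and 2 undergo a harvest (6.2.2), and every Arm 3 subject has blood drawn for the immunogenicity test (8.2.15.4). Giving the coordinator the product at screening weakens this protection in three ways.

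- **Selective loss before injection.** Day 0 eligibility is re-confirmed when the product may already be known at the site. Some criteria are matters of judgement (exclusions 16 and 19 in 5.1.2), and 7.1 allows withdrawal for administrative reasons.
- **Leakage to the subject.** Staff who know the product deal with the subject from screening onward, including the regular contacts in 6.3 and the physical-therapy review in 8.1.3.
- **Interviewer influence.** If the Month 9 scores are taken orally, the caller may know who received steroid. Month 9 is a level in the treatment-by-time test, which 9.3.2 makes the overall hypothesis test.

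**Working it through.** **Step 1. Order of events.**

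| Step | Section | Product known to coordinator? |
|---|---|---|
| Full eligibility confirmed | 4.3, 8.1.1 | No |
| Randomisation; assignment link issued | 6.2.1, 8.1.1, 1.3 | Yes, from here |
| Procedure scheduled from the result | 8.1.1 | Yes |
| Eligibility re-confirmed, Day 0 | 1.3 footnote p, 8.1.2 | Yes |
| Injection, Day 0 | 8.1.2 | Yes |
| Outcomes at Months 1, 3, 6, 9, 12 | 1.3, 8.1.4 to 8.1.8 | Not excluded |

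Section 6.2.1 does not say that the coordinator is at the site. That is inferred from 8.1.1, where the site schedules from the randomisation result.

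**Step 2. Is the product needed at screening?** In Arms 1 and 2, Section 8.1.2 gives cell and steroid subjects the same harvest, processing and release testing; only the steroid preparation differs. The Arm is enough to schedule them. For Arm 3 the documents do not settle the matter: 4.1 and 6.1.3 describe shipment and thawing but not whether doses are stocked at the site or sent per subject.

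**Step 3. The plan's own figures.** Inputs from 9.2: VAS difference 1.5, SD of change 3.5, KOOS difference 10, SD 20, n = 121 per group, two-sided 5% t-test. Recomputed power is 91.3% for VAS and 97.2% for KOOS, against 91% and 97% stated. Both reproduce.

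**Step 4. Illustration of the Month 9 exposure.** The documents give no interviewer effect. Assume no true difference and a shift b of 0.25, 0.5 or 0.75 VAS points between a cell group and steroid, at Month 9 only.

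- SE = 3.5 × √(2/120) = 0.452.
- Planned pairwise level (9.3.2): 0.05/6 = 0.0083, critical z = 2.638.
- Rejection rate = P(|Z + b/SE| > critical value). The rates below use the t-test version.

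| b | b/SE | Rejection at 0.0083, n = 120 | Same, n = 108 (90% retention) |
|---|---|---|---|
| 0 | 0 | 0.8% | 0.8% |
| 0.25 | 0.55 | 1.9% | 1.8% |
| 0.5 | 1.11 | 6.2% | 5.5% |
| 0.75 | 1.66 | 16.1% | 14.1% |

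These rates are for one cell-versus-steroid comparison. Under 9.3.2 the pairwise tests run only after a significant interaction or treatment main effect, so the rate in the full sequence cannot exceed them.

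**Step 5. The overall tests.** For the interaction test, further assume compound symmetry and the same shift in all three cell groups.

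- Residual variance = 3.5²/2 = 6.125.
- Degrees of freedom = 3 × 5 = 15.
- Noncentrality = 120 × b² × 0.75 × (5/6) / 6.125 = 12.24 b². Here 0.75 is the sum of squared deviations of (1, 1, 1, 0) over groups, and 5/6 is that of one visit among six.
- Rejection at 5% is about 7%, 14% and 31% for the three shifts.

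If instead the contrast averages five follow-up visits equally, the shift becomes b/5. With SD 3.5 kept as a simplification, rejection at 5% is about 5.1%, 5.6% and 6.3%.

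**The case against.** Much can be said for the plan, and several stronger readings fail.

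- **Single-blinding is declared openly, and blinded subjects report the outcome.** This stands. The point is a missing safeguard, not a contradiction.
- **A reader might infer that a VAS cannot be completed on a call, so the score must be spoken to an interviewer.** Sections 4.1 and 8.0 say subjects fill out the forms at each time point, and 8.1.7 gives no mode. Only the absence of a stated mode is supported.
- **A reader might infer that subjects can be enrolled or dropped freely once the product is known.** Full eligibility is confirmed before randomisation (4.3, 6.2.1, 8.1.1), so Day 0 is a re-check. Section 9.3 requires intention-to-treat analysis of all randomised subjects, although that helps only if outcomes are still collected after exclusion. The time at risk is also uncertain: the 30-day limit in 4.3 runs from consent to randomisation, not from randomisation to injection.
- **A reader might infer false-positive rates of about 9%, 20% and 38%.** Those follow from an unadjusted 5% contrast at Month 9, which 9.3.2 does not contain.
- **A reader might infer that sites never need the Arm 3 product before Day 0.** The documents do not say that UCT doses are held at the site.
- **The Operations Manual, or the SAP detail to which 6.2.1 defers, may name blinded collectors.** Neither is available here. If they do, a sentence in the protocol would largely settle the question of who collects the scores, but not the timing of release.

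**Conclusion.** The point holds as a gap that is cheap to close. The coordinator receives the product assignment earlier than Arms 1 and 2 require and before the Day 0 re-check. The available documents neither keep holders of the assignment away from outcome collection nor say how the Month 9 scores are obtained.

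The telephone part concerns one of five follow-up pain scores. The 12-month score, on which the sample size rests, is taken at an in-person visit. Whether any bias would occur, and how large it would be, is unknown. The range of about 2% to 16% for a Month 9 pairwise test at 0.0083 depends wholly on the assumed shift of 0.25 to 0.75 points, SD 3.5 and 120 per group. The planned overall tests give anything from almost no inflation (visit average) to about 31% (interaction test, largest shift). No figure can be put on selective exclusion or leakage from these documents.

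Confidence is medium, because the coordinator's site role is inferred and the operational documents are unseen.

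**What to change.** 1. **Sections 6.2.1 and 8.1.1.** Release only the Arm (1, 2 or 3) to the coordinator at screening. Have the EDC release cell versus steroid on Day 0, after the eligibility form is signed, and only to the staff who prepare and inject. In Arm 3, if UCT doses are shipped per subject, release the product earlier only to the staff who handle supply.
2. **Sections 8.1.7 and 8.2.11.** Have subjects complete VAS and KOOS themselves on the same form at every visit where these outcomes are due, by mail or electronic link at Month 9. Use the Month 9 call for adverse events, medications and a reminder to return the form.
3. **Section 6.2.2.** State that staff who know the product do not collect or prompt the patient-reported outcomes at any visit. This is needed besides item 1, because those who prepare and inject still learn the product on Day 0, and later release alone does not determine who telephones at Month 9.

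**Cost.** An EDC role and timing setting, a mailed or electronic form, protocol wording, and a division of duties among existing staff. The downsides are possibly slightly lower Month 9 completion and some coordination on Day 0 or in Arm 3 supply.

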### **6.2.2 Implementation of Randomization and Blinding**

Subjects randomized to Arm 1 or Arm 2 will undergo a procedure (bone marrow aspiration or liposuction) but will only receive one of the possible injections. For instance, subjects randomized to the control portion of Arm 1 will undergo a bone marrow aspiration but will receive a blinded corticosteroid injection. The bone marrow aspirate will still be processed and used to help quantify cell characteristics. Subjects randomized to Arm 3 will not undergo the procedures mentioned above. They will be blinded and receive either the stem cell injection or the corticosteroid injection.

Four hundred eighty subjects will be randomly assigned to treatment in this multicenter trial. Subjects at each clinical site will be randomized to ensure the trial is single-blind with a 1:1 allocation ratio across the four treatment groups.

One hundred twenty subjects will be randomized at each of 4 clinical sites. Arm 1: Forty subjects will be randomized with a 3:1 allocation ratio (bone marrow derived MSCs versus corticosteroid injection; 30:10). This same implementation plan will be used to randomize 40 subjects to Arm 2 (adipose derived MSCs versus corticosteroid injection) with a 3:1 allocation ratio and to randomize 40 subjects to Arm 3 (umbilical cord tissue MSCs versus corticosteroid injection) with a 3:1 allocation ratio.

### **6.3 Study Compliance**

Subjects will be contacted regularly by study team members with appointment reminders to aid in compliance with the protocol. Subjects will be encouraged to contact the investigator or study staff in between follow-up visits to report AEs and SAEs in a timely manner.

### **6.4 Concomitant Therapy**

Concomitant therapy will not be utilized during the study as described in sections 5.1 and 5.2. Any interventions the subject may require after the study injection, will be monitored and recorded during follow-up visits. Concomitant therapies such as anti-inflammatories, pain medication, injections and surgery will be recorded on the Concomitant Medications and Treatments log.

## **7.0 Subject Discontinuation/Withdrawal**

### **7.1 Subject Discontinuation**

A subject must be discontinued from the trial for any of the following reasons:

- Unacceptable adverse experience
- Investigator's decision to withdraw the subject for safety, behavioral, compliance, or administrative reasons
- If the BMAC, SVF final products or UCT MSCs do not meet final product acceptance criteria outlined in the Operations Manual

For those subjects who discontinue participation early, each subject will be followed for serious adverse events (90 days) that are ongoing at the time of subject discontinuation. Monitoring of the serious adverse event may be done by telephone per treating investigator discretion. All AEs potentially related to study participation will be followed until resolution prior to study completion or early termination of subject. Open AEs that are unrelated to the study participation will not be followed beyond study completion or subject's early termination.

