#### **7.4 Treatment Failure**

In order to reduce bias, if subjects require concomitant therapy (i.e. other injections), pain scores and subsequent treatment information will continue to be collected through the 1-year follow up after a subject is declared a treatment failure.

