#### **8.4.3 AE and SAE Collection**

All AEs and SAEs will be collected from the signing of the informed consent form until the one-year follow-up visit at the time points specified in the SoA (Section 1.3) as required by applicable regulation and best practice.

All SAEs will be recorded and reported to the sponsor and the pharmacovigilance team at Advanced Clinical within 24 hours of the study personnel becoming aware of the event. Please utilize the approved SAE data collection forms provided by Advanced Clinical to submit the notifications and updates. The investigator will submit any updated SAE data to the sponsor within 24 hours of it being available.

Investigators are not obligated to actively seek AE or SAE after conclusion of the study participation. However, if the investigator learns of any SAE, including a death, at any time after a subject has been discharged from the study up to a 30 day follow-up period, and he/she considers the event to be reasonably related to the study intervention or study participation, the investigator must promptly notify the sponsor.

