#### **8.4.4 Follow-up of AEs and SAEs**

After the initial AE/SAE report, the investigator is required to proactively follow each subject at subsequent visits/contacts. All AE/SAEs, will be followed until resolution, stabilization, the event is otherwise explained, or the subject is lost to follow-up (Lost to follow-up is defined in Section **Error! Reference source not found.** of the protocol).

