### **9.3 Efficacy Analyses**

The statistical analysis plan (SAP) has been developed and describes the subject populations to be included in the analyses, and procedures for accounting for missing, unused, and spurious data. This section is a summary of the planned statistical analyses of the primary and secondary endpoints.

The primary analysis of the data will be performed according to subjects' original treatment assignment (i.e., intention-to-treat analyses) regardless of their compliance to treatment and the inclusion of all data from all subjects randomized in the final analysis.

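### Section 7.1 ends trial participation for adverse-event or safety reasons after a one-time injection and has no rule keeping those subjects in safety and outcome collection to one year

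*Combined protocol and SAP*

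**What the plan says.** Section 7.1 opens with "A subject must be discontinued from the trial for any of the following reasons". The first reason is "Unacceptable adverse experience", which the protocol does not define. The second is an investigator's decision to withdraw the subject, with safety among the grounds. The third, failure of product acceptance criteria, is a separate route and outside this point.

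Section 7.1 then sets three follow-up rules for subjects who leave early:
- **SAEs:** "each subject will be followed for serious adverse events (90 days) that are ongoing at the time of subject discontinuation", by telephone if the investigator prefers.
- **Potentially related AEs:** followed until they resolve. The same sentence places this before study completion or early termination, so it is unclear whether it continues after exit.
- **Unrelated open AEs:** not followed past early termination.

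Other sections say:
- **6.2.2:** each subject "will only receive one of the possible injections" (written of Arms 1 and 2; Arm 3 subjects likewise receive either cells or corticosteroid). The Schedule of Activities places the injection on Day 0.
- **1.1:** everyone randomized is followed for about a year after treatment.
- **8.4.3:** "All AEs and SAEs will be collected from the signing of the informed consent form until the one-year follow-up visit". The section also frees investigators from actively seeking events once participation has ended, and asks them to report related SAEs that they learn of within 30 days of discharge.
- **8.4.4:** AEs and SAEs "will be followed until resolution, stabilization, the event is otherwise explained, or the subject is lost to follow-up".
- **7.4:** pain scores and treatment information "will continue to be collected through the 1-year follow up after a subject is declared a treatment failure", with bias reduction as the stated reason.
- **9.3:** the intention-to-treat analysis calls for "the inclusion of all data from all subjects randomized in the final analysis".
- **1.3, footnote m, and 8.1.10:** the End of Study visit takes place only if the whole study stops early.

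**The concern.** Once the single injection has been given, no study treatment remains to be stopped. Discontinuing the subject from the trial therefore ends observation and nothing else, and the trigger is harm.

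Two things are at stake. The first is safety. Later events that are new, distinct or worse than the one that led to exit would not be actively sought in the subjects who have already had trouble. Section 2.3.1 lists harms that could appear or persist late, such as bone necrosis and nerve injury after steroid injection, and lasting swelling or revision surgery after liposuction. The 12-month antibody sample could also be lost in umbilical cord recipients who reacted.

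The second is efficacy. The mixed model in 9.3.2 excludes missing values and relies on their being non-informative. Loss caused by a bad experience strains that assumption. Section 9.3 refers to a statistical analysis plan for handling missing data, but no analysis recovers data that were not collected.

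There is also a conduct problem: two sites could handle the same subject differently, and each could cite the protocol.

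**Working it through.** **1. The passages side by side, for an injected subject who leaves under the first or second reason in 7.1.**

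| Item | After exit under 7.1 | Elsewhere |
|---|---|---|
| SAE ongoing at exit | 90 days | 8.4.4: to resolution or stabilization, no 90-day limit |
| Related AE ongoing at exit | until resolved, on one reading | 8.4.4: same end point as above |
| Unrelated AE ongoing at exit | dropped | 8.4.4: no relatedness limit |
| New AE or SAE | not actively sought; 8.4.3 asks for related SAEs learned of within 30 days of discharge | 8.4.3: general window runs to the one-year visit |
| PROs, MRI, antibody sample | no provision | 1.1: about one year for all randomized; 9.3: all data from all randomized |
| Exit visit | none | 1.3 and 8.1.10: only if the study stops |

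The PRO, MRI and antibody row is an inference from exit being from the trial and from the absence of any retention rule. No sentence states it.

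**2. Observation time lost.** The exit day d is an assumption. For new events, days lost = 365 − d. For an SAE ongoing at exit, if the 90-day limit governs, days lost = 365 − d − 90.

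| Exit day | New events | Ongoing SAE |
|---|---|---|
| 7 | 358 (98%) | 268 (73%) |
| 30 | 335 (92%) | 245 (67%) |
| 90 | 275 (75%) | 185 (51%) |
| 180 | 185 (51%) | 95 (26%) |

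The last column does not apply to a related SAE if the related-AE sentence continues after exit.

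**3. Power is not the issue.** The inputs from 9.2 are n = 121 per group, two-sided 5%, a VAS difference of 1.5 with SD 3.5, and a KOOS difference of 10 with SD 20. The noncentrality is difference / (SD × √(2/n)): 1.5 / (3.5 × 0.1286) = 3.33 for VAS and 10 / (20 × 0.1286) = 3.89 for KOOS. The t-test power is 91.3% and 97.2%, which reproduces the stated 91% and 97%. At the expected 90% retention, 120 × 0.90 = 108 per arm, and power is 88.0% and 95.5%. What matters is who is lost.

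**4. Illustration of selective loss.** Suppose a fraction f of an arm leaves for harm, and their 12-month VAS change would be D points worse than that of the rest. The mean of those remaining is then too favourable by f × D. Neither f nor D is in the documents.
- f = 2%, D = 1.5: 0.02 × 1.5 = 0.03 points.
- f = 5%, D = 2.5: 0.05 × 2.5 = 0.125 points.
- f = 10%, D = 3.5: 0.10 × 3.5 = 0.35 points. Here f takes up all of the 10% loss that 9.2 expects.

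The shift in the contrast between a cell arm and control is f(cell) × D(cell) − f(control) × D(control). With f = 5% and D = 2.5 in both arms it is 0.125 − 0.125 = 0. With 5% against 2% it is 0.125 − 0.05 = 0.075 points, or 0.075 / 1.5 = 5% of the planned difference.

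**The case against.** Several stronger readings are tempting, and the documents do not support them.

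- **That 7.1 follows nothing but SAEs already ongoing.** The same paragraph says potentially related AEs are followed until they resolve. Its end point is ambiguous, which calls for clarification, but it does not show that related events are abandoned. Harms of the procedure or injection that began before exit may be covered.
- **That 7.1 flatly contradicts 8.4.3.** Section 8.4.3 itself ends the duty to seek events when participation ends and adds the 30-day reporting of related SAEs. The one-year window is in tension with 7.1. The firm conflicts are with 1.1, 8.4.4 and 9.3.
- **That 7.1 contradicts 7.4.** Section 7.4 covers subjects who need other therapy, which is a different group. It is a contrast that shows the sponsor knew the remedy.
- **That one-year AE rates are biased downward across the board.** Sections 9.4.2 and 9.4.4 count subjects with events, and the event that led to exit is already counted. Under-counting is confined to later distinct or worsening events.
- **That the pain effect is overstated by a known amount.** The discontinuation rate is not given, 7.1 applies to every arm, and control subjects in Arms 1 and 2 also undergo harvest. The repeated-measures model also keeps visits made before exit, so step 4, which treats the analysis as one of 12-month completers, is closer to an upper bound for its inputs.

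All of these limits stand. None of them supplies active collection of new events, outcome data or an exit visit after discontinuation.

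**Conclusion.** The point holds in a limited form. Section 7.1 requires exit from the trial for adverse-event or safety reasons when only observation remains to be ended, and it has no rule for retaining those subjects. It cannot be applied together with 1.1, 8.4.4 and 9.3 as written. Missingness would then depend on harm, against the assumption in 9.3.2.

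The effect on the results cannot be sized from the documents. The day counts rest on an assumed exit day. The VAS illustration (0.03 to 0.35 points in one arm's mean, against a planned difference of 1.5) rests on assumed rates and outcomes, and only loss that differs between arms moves the comparison. The gap in ascertaining late harm is the stronger argument; the efficacy effect is probably modest. This is an inexpensive improvement that should be made. It does not invalidate the design.

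**What to change.** In 7.1, state that an injected subject who meets an adverse-event or safety reason for discontinuation stays in the scheduled data collection through Month 12 unless consent is withdrawn. That means AEs and PROs, with MRI and antibody testing where applicable. The statement should cover both the first reason and the investigator's safety withdrawal. Deleting the first reason alone would leave the second as the same way out.

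Reconcile 7.1 with 1.1, 8.4.3, 8.4.4 and 9.3 so that one AE/SAE follow-up rule applies, and say plainly whether follow-up of related AEs continues after exit. This concerns data collection; clinical care of the event stays with the investigator.

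The cost is a wording amendment and, for what are likely to be few subjects, visits already in the schedule.
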